5.1. Data Management

Data handling and transfer will take place as described in the Data Management Plan (DMP) for the study.

SDTM datasets will be created based on the raw eCRF and laboratory data and adhere to CDISC SDTM Implementation Guide 3.2. Analysis datasets will be generated using (SAS®) version 9.3 or later software and adhere to ADaM Implementation Guide 1.1 structure.

5.2. Data Presentation Conventions

Unless otherwise stated, continuous data will be summarized with the following descriptive statistics: number of non-missing observations (n), arithmetic mean, standard deviation (SD), median, minimum (min), maximum (max), and for PK parameters only, geometric mean, SD and geometric CV% for continuous variables. Categorical variables are summarized using counts and percentages. All reported p-values will be 2-sided.

The following conventions are applied to all data presentations and summaries.

- For continuous variables, all mean and median values are formatted to one more decimal place than the measured value. Standard deviation values are formatted to two more decimal places than the measured value. Minimum and maximum values are presented with the same number of decimal places as the measured value.
- For categorical variables, the number and percentage of responses are presented in the form XX (XX.X%) where the percentage is in the parentheses.

5.3. Analysis Populations

All populations will be defined after database lock when the relevant data are available.

5.3.1. Intent-to-Treat (ITT)

ITT (Randomized) population will include all subjects who are randomized. Subjects will be analyzed according to the treatment they were assigned.

5.3.2. Modified Intent-to-Treat (mITT)

mITT population will include all subjects who are randomized into the study and have at least 1 post baseline viral RNA assessment. Subjects will be analyzed according to the treatment they actually received.

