10.7.3. Part 1 Analyses

Part 1 will be analyzed separately as an a priori powered study. A Statistical Analysis Plan will be developed that describes the analyses to address the study's primary, secondary, and exploratory objectives.

The following provides an outline of the methods for the main comparisons between randomized arms, particularly for the primary outcome measure.

Analyses involving randomized comparisons will include all randomized participants who received the first (confirmed) dose of study treatment, according to a modified intention-to-treat (m-ITT) approach. Participants who do not receive the first (confirmed) dose will be replaced. Unless stated otherwise, the date of randomization will be the time origin for analysis (Day 1). Additional per-protocol analyses may be performed, particularly for virology efficacy endpoints. Missing data are expected to be uncommon (<5 to 10% of participants). Losses to follow-up will be assumed non-informative and complete-case analyses will be conducted.

This is a virology proof-of-principle study, as such a type I error probability of 10% (α =0.10) will be used throughout, with no planned adjustments for multiplicity or primary or secondary endpoints. Throughout, all statistical tests will be two-sided and "exact" statistical procedures that do not rely on large sample assumptions will be applied where computationally feasible.

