10.7.3.1. Primary Outcome Measures

Virologic Efficacy: The distribution of days until first non-detectable SARS-CoV-2 viral RNA in NP swabs will be estimated for each randomized arm (drug versus placebo), using Kaplan-Meier methods with a corresponding exact stratified log-rank test (Part 1 only: to account for the "early" versus "late" time from symptom onset randomization strata). "Non detectable" will be defined as a viral load below the limit of quantification (BLOQ). Two consecutive non-detectable viral RNAs in NP swabs (or one negative with no further follow-up) will be required to achieve the event. The date of the first non-detectable will be the event date. Participants who prematurely discontinue the study before achieving non-detectable results will have follow-up for efficacy endpoints censored at the date of last measurement. Losses to follow-up will be assumed non-informative.

Safety and Tolerability: In order to measure the safety and tolerability of EIDD-2801, we will estimate by randomization arm the probability of 1) any AEs leading to early discontinuation of blinded treatment (active or placebo), 2) study drug-related discontinuation of treatment, 3) new grade 3 or higher AE (not already present at baseline), and 4) study drug-related new grade 3 or higher AE. The cumulative probability (i.e., risk) of each safety and each tolerability endpoint (4 endpoints) will be estimated using the Kaplan-Meier approach and stratified log-rank test will be employed for between trial arm comparisons (as outlined for the primary efficacy outcome). Follow-up will be right censored at the date of last known status and event times will be the date of first onset of the given endpoint (e.g., time to first AE leading to early discontinuation of blinded treatment).

The safety and tolerability profile of EIDD-2801 in humans is currently not fully characterized and descriptive participant-level listings of safety and tolerability events will be summarized. We will estimate 28-day risk function of each safety and tolerability endpoint with a corresponding 2-sided 90% confidence interval, with focus on the upper confidence limit for interpretation of results. To inform the design of future larger trials we will estimate the difference in probabilities

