1. INTRODUCTION

This SAP describes the statistical methods to be used during the analysis and reporting for study EIDD-2801-2003.

Study measurements and assessments, planned statistical methods, and derived variables are summarized in this plan. Planned tables, figures, and listings are specified. All decisions regarding final analyses, as defined in this SAP document, have been made prior to locking the database.

This SAP should be read in conjunction with the study protocol and electronic Case Report Form (eCRF). Any further changes to the protocol or eCRF may necessitate updates to the SAP. This SAP supersedes the statistical considerations identified in the protocol; where considerations are substantially different, they will be so identified. If additional analyses are required to supplement the planned analyses described in the SAP, they may be performed and will be identified in the Clinical Study Report (CSR).

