7.3. Demographic and Baseline Characteristics

Demographic (age, sex, race, and ethnicity) and baseline characteristics (height, weight, and body mass index [BMI], vital signs, Smoking Status (current Smoker, ex-smoker or Non-smoker), Days from Symptom Onset, D-dimer, CRP levels, WBC absolute neutrophils count and absolute lymphocyte count) will be summarized and listed.

The baseline viral RNA, baseline patient reported symptom will be summarized and listed.

Demographic and baseline characteristics will be summarized for the ITT population by study part and treatment, and separately for the safety population for the pooled analyses.

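### Part 1 mITT efficacy set is grouped by treatment received, while the protocol describes the primary comparison as one between randomized arms

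*SAP*

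**What the plan says.** **The grouping rule.** SAP 5.3.2 defines mITT as "all subjects who are randomized into the study and have at least 1 post baseline viral RNA assessment" and adds "Subjects will be analyzed according to the treatment they actually received". Protocol 10.6 states the same grouping rule, but its membership also requires a baseline viral RNA result.

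**Where mITT is used.** Protocol 10.7.3 says: "Analyses involving randomized comparisons will include all randomized participants who received the first (confirmed) dose of study treatment", and that this is done "according to a modified intention-to-treat (m-ITT) approach". Protocol 10.7.3.1, within the same Part 1 section, says that the distribution of days to first non-detectable viral RNA "will be estimated for each randomized arm (drug versus placebo".

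**The as-assigned set.** SAP 5.3.1 defines an ITT set for which "Subjects will be analyzed according to the treatment they were assigned". The SAP calls on it in two places: the disposition counts in 7.1, and 7.3, where "Demographic and baseline characteristics will be summarized for the ITT population by study part and treatment".

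**The analysis section.** SAP 9.1, which covers the viral RNA and infectious virus analyses, names no population. SAP 1 states "This SAP supersedes the statistical considerations identified in the protocol", and that substantial differences will be identified. SAP 11 lists two changes, the unstratified log-rank test and the dropped safety comparisons. It does not mention grouping.

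**The concern.** Grouping by treatment received is normal for safety. For a test of efficacy it makes group membership depend on something that happens after randomization. A log-rank test then keeps its nominal error rate only on the further assumption that whatever led to the wrong product was unrelated to how fast the participant would clear virus.

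This matters most in Part 1, the only part with a formal hypothesis test (SAP 2.3; protocol 10.5), where the arms are small. The protocol can also be read two ways: 10.6 implies as-treated and 10.7.3.1 implies as-randomized. Because the SAP claims precedence, the as-treated rule would govern a comparison that the protocol presents as randomized.

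The rule is also incomplete. Ten doses are planned (SAP 8.1), and neither document says how to classify someone who received the wrong product for only some of them. Grouping by assignment needs no such judgement.

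**Working it through.** **1. How assigned and received treatment can differ.** Participants who never take the first confirmed dose are not followed and are replaced (protocol 6.1.6.1 and 10.5). The usual gap between assigned and received treatment is therefore closed, and only kit or dispensing errors remain. The documents give no rate for these, so the number of errors, k, is assumed below.

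**2. Size of one error.** 1/22 = 4.5% of a planned Part 1 arm, or 1/19 = 5.3% of the evaluable number per arm in protocol 10.5.

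**3. Inputs for the test.**
- 19 evaluable per arm (protocol 10.5).
- Two-sided alpha 0.10 (protocol 10.7.3), so reject when |Z| > 1.645.
- Swabs on Days 1, 3, 5, 7, 14 and 28 (SAP 3.2.1).
- Placebo detection probabilities at those days from the table in protocol 10.5: 100, 88, 71, 52, 10, 0%.
- Drug curve for the SAP's risk difference of -35%. The table has no such row, so I took placebo minus 35 points after Day 1, floored at zero: 100, 53, 36, 17, 0, 0%.

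The log-rank statistic is Z = Σ(d1j − dj·n1j/nj) / √Σvj, with vj = dj·(n1j/nj)·(1 − n1j/nj)·(nj − dj)/(nj − 1), summed over visits j. The asymptotic test stands in for the exact one. Each setting used 20,000 simulated datasets.

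**4. The plan's own figure.** SAP 3.2.1 gives 88% power at -35%. The simulation gives 89.4%, close enough to use the set-up. (Protocol 10.5 attaches 88% to -30%. That difference is separate and does not bear on grouping.)

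**5. No drug effect: type I error, nominal 0.10.** In the random case, k participants per arm are swapped without regard to outcome. In the worst case, the k slowest clearers of the drug arm are the ones who received placebo and are counted there.

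| k | As assigned, random | As treated, random | As assigned, worst case | As treated, worst case |
|---|---|---|---|---|
| 1 | 0.099 | 0.101 | 0.102 | 0.154 |
| 2 | 0.100 | 0.102 | 0.101 | 0.276 |
| 4 | 0.106 | 0.103 | 0.100 | 0.531 |

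Nearly all of the worst-case excess favours the drug: 0.144, 0.275 and 0.531 of datasets reject in that direction, against about 0.05 expected.

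**6. Risk difference -35%: power with k random swaps per arm.**

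| k | As assigned | As treated |
|---|---|---|
| 0 | 0.891 | 0.891 |
| 1 | 0.813 | 0.890 |
| 2 | 0.712 | 0.894 |
| 4 | 0.462 | 0.896 |

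**7. The m-ITT texts side by side.**

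| Place | Who is in | Grouped by |
|---|---|---|
| Protocol 10.6 | Baseline and at least one later viral RNA result | Received |
| Protocol 10.7.3 | First confirmed dose taken | Not stated |
| Protocol 10.7.3.1 | Not restated | Randomized arm |
| SAP 5.3.2 | At least one post-baseline viral RNA result | Received |

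There are three memberships and two grouping rules for what should be one analysis set.

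**The case against.** The strongest reply is that nothing may ever turn on this. In a double-blind trial where undosed participants are replaced, wrong-product errors should be few, and with none the analyses coincide. If errors are random, as-treated grouping holds alpha at about 0.10 and keeps power near 0.89, while as-assigned grouping loses power. For a virology proof-of-principle study with dose- and exposure-response aims, that is a real argument. The inflated error rates need the slowest clearers in one arm to be the mis-dosed ones, which is an extreme construction. All of this stands, and it limits the size of the point. It does not settle which grouping the formal test uses, and it does not remove the conflict with protocol 10.7.3.1.

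A reader might infer more than the documents support in four ways:
- *That the rule already breaks the randomized comparison.* It does so only if a participant receives the wrong product.
- *That the same argument covers the later parts, where one participant is 1/12 = 8.3% of an active arm.* Parts 2 to 9 have no formal test, and SAP 5 pools them by dose. Protocol 10.8 places the pooled analyses on the as-treated safety population and treats them as estimation.
- *That the SAP expressly assigns the primary endpoint to mITT and bars ITT from efficacy.* SAP 9.1 is silent on population. The link to mITT comes from protocol 10.7.3, and the limited use of ITT is read from where it is named.
- *That the term m-ITT in protocol 10.7.3 itself means analysis as randomized.* That section states no grouping rule. The support comes from the randomized-arm wording in 10.7.3.1.

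**Conclusion.** The point holds as a conditional defect in the one formally tested efficacy comparison, together with an internal conflict that needs a decision. Both documents group mITT by treatment received, the protocol elsewhere describes the Part 1 primary endpoint by randomized arm, and no as-assigned efficacy analysis is specified.

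The effect is zero with no dosing errors. It is negligible for type I error if errors are unrelated to prognosis. At the assumed extreme it is about 0.15 for one error and 0.28 for two, against a nominal 0.10. Those figures rest on assumed error counts, an assumed link to prognosis, 19 per arm, and the asymptotic log-rank test. They bound the risk and do not predict it. The plan's sample size, alpha and stated power are unaffected. The change is worth making because it is nearly free and removes the dependence on that assumption.

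**What to change.** 1. In SAP 5.3.2 and protocol 10.6, state that for the Part 1 efficacy comparison mITT participants are analysed in the arm to which they were randomized.
2. In SAP 9.1, name that population for the Part 1 viral RNA and infectious virus analyses.
3. Reconcile protocol 10.6, 10.7.3 and 10.7.3.1 with SAP 5.3.2, so that there is one membership rule and one grouping rule. The post-baseline RNA requirement is a separate selection after randomization. Changing the grouping does not cure it, so retaining it should be a deliberate choice.
4. Keep as-treated grouping for the Safety and PK sets and for the descriptive pooled analyses in protocol 10.8.
5. If any Part 1 dosing error occurs, add an as-treated sensitivity analysis, with a stated rule for participants who received the wrong product for only part of the course.

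The cost is a few sentences in each document, with no change to sample size or alpha. The one statistical price is dilution under random mis-dosing (power from 0.89 to 0.81 with one swap per arm at -35%). The sensitivity analysis would show it. The decision should be made before Part 1 treatment assignments are unblinded for analysis.

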5.3.3. Safety Population

All subjects who are randomized and take at least 1 dose of study drug. Subjects will be analyzed according to the treatment they actually received. All the safety analyses will be performed using the safety population. The patient diary and clinical outcome (Ordinal Scale Clinical Improvement, medial visit) data will also be analyzed using the safety population.

5.3.4. Per Protocol (PP)

Per protocol population will include subjects in the safety population who have no important protocol deviations leading to exclusion from the PP population and have completed the Day 28 follow-up Visit.

5.3.5. Pharmacokinetic Population

All subjects in the Safety Population with at least one plasma PK concentrations of EIDD-2801/EIDD-1931.

5.3.6. Subgroups

If data permit, efficacy analyses will be performed by the following subgroups:

- Number of risk factors for severe COVID-19: 0, 1-2 or >2
- Age ≥ 65 or < 65
- Presence or absence of SARS-CoV-2 antibodies
- Positive Infectivity at baseline (based on infectious virus isolation determined by isolation in Vero cell line culture)

The risk factors for severe COVID-19 are:

- Have a body mass index (BMI) \geq 35
- Have chronic kidney disease
- Have diabetes
- Have immunosuppressive disease
- Are currently receiving immunosuppressive treatment
- Are ≥ 65 years of age
- Are ≥55 years of age AND have cardiovascular disease, OR hypertension, OR chronic obstructive pulmonary disease/other chronic respiratory disease

Additional COVID risk factors (i.e., cancer, pregnancy etc.), demographic and baseline characteristics may be explored as subgroups or as covariates for between treatment comparisons.

5.4. Baseline Definition

The baseline is defined as the last assessment prior to the first dose of study medication (i.e., measured at Day 1 pre-dose or at the screening visit).

5.5. Derived and Transformed Data

5.5.1. Study Day

If the date of interest occurs on or after the first dose date then study day will be calculated as:

• (date of interest – date of first dose) + 1.

If the date of interest occurs prior to the first dose date then study day will be calculated as:

• (date of interest – date of first dose).

There is no study day 0

5.5.2. Change from Baseline

Change from baseline is calculated as (post-baseline result – baseline result).

Percent change from baseline is calculated as (change from baseline/baseline result * 100).

If either the baseline or the post-baseline result is missing, the change from baseline and/or percentage change from baseline is set to missing as well.

5.5.3. Derived Endpoints

• SARS-CoV-2 RNA

Efficacy Endpoint of SARS-CoV-2 RNA will be converted to log₁₀ scale. Listings will include the values in log₁₀ scale and in the original scale. For SARS-CoV-2 RNA values reported as below the limit of detection/quantification (the lower limit of quantification is 1018 copies/mL), 1017 copies/mL will be used in the analyses.

SARS-COV-2 RNA below the limit of detection/quantification will be considered as undetectable (negative) in the analyses.

• SARS-CoV-2 RNA Rate of Decline

The individual rate of SARS-CoV-2 RNA decline will be derived as Average Area under the Curve minus Baseline (AAUCMB, i.e., the average daily viral load value minus baseline) for the five time intervals of: D1-D3, D1-D5, D1-D7, D1-D14 and D1-D28 using the following formulas:

AAUC =
$$\frac{\sum_{i=1}^{n-1} (t_{i+1} - t_i) (\frac{x_{i+1} + x_i}{2})}{(t_n - t_1)} = \frac{AUC}{(t_n - t_1)}$$
, and
AAUCMB=AAUC – Baseline (x at time i=1)

where, x_i is the data value at the ith time point and t_i is the time value at the ith time point.

• Time to non-detectable SARS-CoV-2 viral RNA in NP swabs based on PCR

Two consecutive undetectable viral RNAs in NP swabs (or one negative with no further followup) will be required to achieve the event. The date of the first undetectable result will be the event date. If the subject only has undetectable viral RNA at the last on study assessment, it will be counted as event at the time of the last assessment. Subjects not achieving the event and who complete the study follow-up will be censored at the last viral RNA assessment. Subjects not achieving the event and dropped out before Day 28 will be censored at Day 28.

Time to un-detectable = Date of Event (Censored) – date of first dose+1

• Time to negativity of infectious virus isolation in NP swabs based on infectious virus isolation determined by isolation in Vero cell line culture

This endpoint will be derived similarly to time to undetectable viral RNAs in NP swabs based on PCR. Infectious virus will be measured at Days 1, 3, 5, and 7 and additional details will be provided in the CSR.

• Time to COVID Symptom Resolution:

Time to COVID Symptom Resolution will be derived based on subject overall assessment of COVID symptoms with resolution defined as 3 consecutive assessments in a resolved state. For subjects with mild, no symptoms or no diary data at the baseline, the time to resolution is defined as the first time where subject overall assessment is no symptoms for 3 consecutive assessments . For subjects with moderate or higher severity at the baseline, the time to resolution is defined as the first time where subject overall assessment is mild or no symptoms for 3 consecutive assessments. Subjects who completed study and have reached the resolved state on the last 2 assessments will be considered as resolved on the day prior to the last assessment. Subjects who completed study and have reached the resolved state will be considered as resolved on the last assessment will be considered as resolved on the last assessment will be considered as resolved state on the last assessment will be considered as resolved state on the last assessment will be considered as resolved state on the last assessment will be considered as resolved state on the last assessment will be considered as resolved state on the last assessment will be considered as resolved state on the last assessment will be considered as resolved state on the last assessment will be considered as resolved state on the last assessment will be considered as resolved state on the last assessment will be considered as resolved state on the last assessment will be considered as resolved state on the last assessment will be considered as resolved state on the last assessment will be considered as resolved state on the last assessment will be considered as resolved state on the last assessment will be considered as resolved on the date of the last assessment.

Subjects not achieving symptom resolution and completing the study will be censored at date of last COVID symptom diary. Subjects not achieving the event and dropped out before Day 28 will be censored at Day 28. Subjects who do not achieve the event and do not complete the day 28 diary due to hospitalization will be censored at day 28.

Subject diary data collected within 28 days of first dose will be included in the derivation of the time to COVID symptom resolution endpoint.

Time to resolution (days) = Date of resolution (Censored) – date of first dose+1

• Time to patient reported general physical health of 3 or 4 (Very Good or Excellent)

This endpoint will be derived similarly to the time to symptom resolution.

• Time to patient reported returned to the (Pre-COVID) health

This endpoint will be derived similarly to the time to symptom resolution.

• Time to resolution of upper respiratory tract symptoms (based on the worst severity of the 5 symptoms measured: Cough, Shortness of breath, Sore throat, Nasal obstruction and Nasal discharge)

This endpoint will be derived similarly to the time to symptom resolution.

• Time to resolution of common COVID symptoms (based on the worst severity of the 13 symptoms measured: Cough, Shortness of breath, Feeling feverish, Muscle aches, Diarrhea, Vomiting, Nausea, Headache, Sore throat, Nasal obstruction, Nasal discharge, Fatigue and Chills)

This endpoint will be derived similarly to the time to symptom resolution.

• Time to resolution of common COVID symptoms (based on the worst severity of the 12 symptoms measured: Cough, Shortness of breath, Feeling feverish, Muscle aches, Diarrhea, Vomiting, Nausea, Headache, Sore throat, Nasal obstruction, Nasal discharge and Chills)

This endpoint will be derived similarly to the time to symptom resolution.

• Time to resolution of Cough

This endpoint will be derived similarly to the time to symptom resolution.

• COVID related medical visit

A subject is considered to have a COVID related medical visit if the subject meets any of the following:

- 1. Hospitalized based on the Hospitalization CRF or any outpatient medical visit (including telemedicine visits)
- 2. Answered "Yes" to the Diary question 'Sought urgent medical care at an emergency room or clinic'
- 3. Answered "Yes" to the Diary question "Been hospitalized for at least 24 consecutive hours"

